1.3.6 Potential Safety Concerns

In general, MSC infusion in humans, including allogeneic MSCs, has been very well tolerated. Autologous MSC infusion is not an option for this clinical trial due to the underlying genetic defect. Neither acute nor long-term clinically significant AEs attributable to allogeneic MSCs have been reported. Up to 1 x 10⁷ cells/kg can be infused safely (our study will infuse up to a maximum of 5 x 10⁶ cells/kg)³⁷. There have been no reports of immunosuppression attributed to MSC infusion leading to opportunistic infection or autoimmunity reaction. In one clinical trial a subject developed urticaria with the second infusion of allogeneic MSCs, thought to be due to development of antibodies to the fetal bovine serum (FBS) used to culture MSCs⁵⁸. FBS will not be used in this protocol. There have been no reports of *de novo* neoplasm in recipients, either potentially derived from MSCs or due to a permissive effect of MSCs. MSCs are immune privileged and therefore infusion of allogeneic cells is possible. There have been no pulmonary complications. Nevertheless, several potential adverse effects will require close attention.

1.3.6.1 Infusion-Related Toxicity

During this study, we plan to use freshly expanded hMSCs. By using freshly expanded hMSCs for the infusions, possible infusion-related toxicities will be reduced. However, there is a possibility that a subject may be unable to get fresh hMSCs on the day of the infusion. In this instance, we may infuse expanded hMSCs that have been frozen with dimethylsulfoxide (DMSO). Most studies have reported no infusion-related AEs. A patient with encephalopathy, stroke, and myocardial infarction most likely related to DMSO used in freezing medium has been reported⁵⁹. Anti-FBS antibodies are common but usually not clinically significant⁶⁰. One study reported a single participant who developed an urticarial rash following a second allogeneic MSC infusion⁵⁸. That participant had a 150-fold increase in anti-FBS antibodies after the second infusion. Because MSCs are relatively large cells (20-60 μ m)⁶¹ and cell clumping is possible, pulmonary embolism is a potential concern. No study has reported pulmonary symptoms, change in oxygen-saturation, or change in chest radiograph. Adherence to established procedures for thawing and infusing cells should minimize the potential for these AEs.

1.3.6.2 Infection

MSC infusion *per se* could be a source of infection. MSCs could be contaminated during harvest, manipulation, or infusion. One case series reported a subject with GVHD who developed central line infection and cellulitis⁶², not uncommon in critically ill patients. Aseptic technique during BM aspiration and infusion, strict adherence to culture protocols, and stringent microbiologic screening are intended to minimize the risk of administering a contaminated cell product. Furthermore, MSCs are potently antimicrobial as previously discussed. Therefore, using our established good laboratory practices and extensive experience in infection control and conduct of clinical trials will minimize the potential risk of infection.

MSCs express CD13 (the cytomegalovirus (CMV) receptor) and to a lesser extent CD21 (the receptor for EBV)⁶³. MSCs can be infected *in vitro* with CMV and HSV-1 but not EBV. Reassuringly, CMV, HSV-1, HSV-2, EBV, VZV RNAs were not detected by PCR in MSCs from seropositive donors. Nevertheless, careful donor screening for herpes virus, cytomegalovirus and other infectious agents in potential future studies of allogeneic MSC infusion will remain important.

Finally, because of the immunosuppressive actions of MSCs, recipients potentially are at increased risk for more severe or opportunistic infections. MSCs inhibit lymphocyte proliferative responses to herpes viruses, candida, and *S. aureus* Protein A⁶³. MSC effects on virus-specific T-cell responses appear to be less than on other immune responses, e.g. to alloantigens⁶⁴. Infections have occurred in a significant proportion participants receiving MSC infusion in some series. However, all of the reported cases have involved already immunocompromised patients with cancer and/or GVHD following HSC infusion⁶⁵⁻⁶⁷. Therefore, it is difficult to discern whether MSC infusion played a role in the infections. Furthermore, MSCs themselves are antimicrobial, producing peptides which aide in clearance and managing infections.

1.3.6.3 Cancer

The potential for malignant transformation would not be unexpected given some of the biologic similarities between stem cells and cancer cells. MSCs in adults may become tumorigenic^{68,69} and have been implicated in several human or experimental tumors, including childhood leukemia⁷⁰, gastric epithelial cancers⁷¹ and osteogenic sarcoma⁷². In the study by Tolar et al.⁷², the high frequency of osteogenic sarcoma in lung after MSC infusion in mice appeared to be related to the propensity of mouse cells to develop frequent karyotypic abnormalities even with short-term culture. Karyotypic abnormalities were not seen in some studies of human MSCs⁷³ but were reported in others, predominantly with prolonged culture⁷⁴⁻⁷⁶. An important factor appears to be continuing cultures following senescent crisis^{77,78}.

A number of studies demonstrate homing of MSCs to primary and metastatic cancers where they may form tumor stroma⁷⁹. In addition, trophic or immunosuppressive effects of MSCs could create a permissive environment for cancer development. For example, MSC-derived adipocytes reduced apoptosis of acute promyelocytic leukemia cells in culture⁸⁰. MSCs promote experimental breast cancer metastasis in mice⁸¹. Human MSCs mixed with human breast cancer cells injected SC as xenograft in mice led to marked increase in metastatic potential. MSCs prolonged B16 melanoma tumor cell survival when co-injected subcutaneously in mice⁸². In a randomized trial in hematologic malignancy of HLA-identical sibling matched HSC +/- MSC, there was decreased GVHD in MSC recipients (11.1% vs. 53.3%) but increased leukemia relapse (6/10 (60.0%) vs. 3/15 (20.0%))⁶⁶.

Despite these theoretical concerns, there have been no reports of *de novo* tumor formation complicating MSC infusion in humans in the more than 500 MSC clinical trials documented in Clinicatrials.gov. Nevertheless, cells will be passaged the minimum number of times to obtain sufficient cell yield to lessen potential for cytogenetic abnormalities. Also, in this trial participants with a history of invasive cancer requiring systemic therapy will be excluded.

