A significant concern in CF patients receiving potent anti-inflammatory drugs is the increased risk of pulmonary exacerbations. Weiss and colleagues performed a placebo-controlled, randomized trial of mesenchymal stem cells in COPD where 31 subjects received four monthly stem cell infusions and there was no difference in hospitalizations for COPD exacerbations during the study (six in the MSC group and five in the placebo group)²³. A recent meta-analysis did not detect an association between MSC treatment and the development of infection²². Preliminary data in CF animals suggest improvement in infection related outcomes, not worsening^{18,19}. In our studies of CF mice infected with *P. aeruginosa*, there was a decrease in the bacterial burden in the animals that received hMSC infusions (Figure 1). No secondary spread or infectious complications were noted.

Another potential concern is the possible increased risk of cancer. Again, this has not been detected in clinical trials^{22,24}. However, the potential for malignant transformation would not be unexpected given some of the biologic similarities between stem cells and cancer cells. The risk of tumorigenesis is likely to be an extremely uncommon event with current culture conditions where cells are harvested for therapy well before the cultures reach senescence²⁰. Another potential risk could result if hMSCs engrafted for long periods of time leading to ectopic tissue formation and increased risk of malignant transformation. Autopsy studies did not detect hMSCs in follow-up studies. It appears that hMSCs work through a “hit and run” mechanism²¹. Despite these theoretical concerns, there have been no reports of *de novo* tumor formation complicating MSC infusion in humans^{22,24}. Nevertheless, in our protocol, cells will be passaged the minimum number of times to obtain sufficient cell yield to lessen potential for cytogenetic abnormalities, and any potential CF subjects with a history of invasive cancer requiring systemic therapy will be excluded from the study.

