6.3 Exclusion Criteria

1. Use of an investigational agent within the 4-week period prior to Visit 1 (Day -42 to -10)
2. Chronic daily (>10 mg) or alternate daily (>20 mg on alternate days) use of systemic corticosteroids within the 4 weeks prior to Visit 1 (Day -42 to -10) or initiation of any dosage of systemic corticosteroids within 72 hours prior to Visit 2 (Day 1)
3. Use of hydroxychloroquine or immunosuppressants
4. Initiation of a new antibiotic (oral, IV, and/or inhaled) that is not part of the subject's maintenance regimen for treatment of acute respiratory symptoms within 2 weeks prior to screening through Visit 2 (Day 1)
5. Initiation of any new chronic therapy (e.g., Pulmozyme[®], hypertonic saline, Kalydeco[®], Orkambi[®], high-dose ibuprofen azithromycin, TOBI[®], Cayston[®], nebulized colistin, bronchodilators, inhaled corticosteroids, etc.) within 4 weeks prior to screening
6. Active treatment for non-tuberculous *Mycobacteria*
7. History of a sputum culture positive for a *Burkholderia cepacia* complex organism in the previous 12 months
8. Current tobacco smoker
9. Oxygen saturation $< 92\%$ on room air at Visit 1 (Day -42 to -10)
10. History of pulmonary hypertension
11. SGOT (ALT) or SGPT (AST) > 2.5 times the upper limit of normal at screening, documented biliary cirrhosis, or portal hypertension
12. Total bilirubin concentration >1.2 mg/dL at screening
13. Creatinine > 1.8 mg/dL at screening
14. Pregnant, breastfeeding, or unwilling to practice birth control between Visit 2 (Day 1) and Telephone Call 3 (Day 56) (acceptable forms of contraception: abstinence, hormonal birth control, intrauterine device, or barrier method plus a spermicidal agent), unless surgically sterilized or postmenopausal
15. Screening hematology with white blood cell count $< 4.5 \times 10^9$ cells/L, hematocrit $< 30\%$, and platelets $< 150 \times 10^9$ platelets/L
16. History of invasive cancer requiring systemic therapy
17. History of organ transplantation
18. Currently listed for lung transplantation or having potential to be listed for lung transplantation in the succeeding 12 calendar months from screening
19. Subject unlikely to complete the study as determined by the Investigator

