The risks of a bone marrow aspiration include pain at the time of the aspirate, which is common but well controlled with adequate use of Xylocaine, bupivacaine and morphine. Other risks include bleeding, infection at the site of the aspirate, and occasional lightheadedness or fainting due to a vasovagal reaction after the procedure. Healthy volunteers and subjects with CF, who undergo the optional bone marrow examination, will be followed by the study PI or designee for AEs related to the procedure.

Inclusion Criteria for Healthy Volunteer Donors:

- 1) Male/female age \geq 18 years
- 2) Able to understand and sign ICF (a legally authorized representative will not be permitted)

Inclusion Criteria for CF Donors:

- 1) CF subject enrolled in the main study and consented to this optional procedure

Exclusion Criteria for both Healthy Volunteer Donors and CF Donors:

- 1) Fever or current illness on the day of the cell collection
- 2) Evidence of communicable disease.
- 3) Any significant change in health status within 2 weeks prior to cell collection that the PI/Sub-Investigator deems relevant to exclude participation
- 4) Subject-reported history of organ transplantation
- 5) Subject-reported history of HIV, hepatitis B or C, or syphilis
- 6) For HV donors only, subject-reported known history of being diagnosed with cystic fibrosis (CF) or being a CF carrier (one copy of CF gene mutation)
- 7) Positive screening blood test result for any infectious disease.
- 8) For HV donors only, positive test result for CMV or a CF gene mutation.
- 9) Pregnant, planning a pregnancy, or breast-feeding at screening.

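### Exclusion 16 covers only invasive cancer that requires systemic therapy, while the tumour hazard described in section 1.3.6.3 does not depend on how a cancer is treated

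*Combined protocol and SAP*

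**What the plan says.** The operative rule is item 16 of the exclusion criteria in section 6.3: "History of invasive cancer requiring systemic therapy". The synopsis uses the same words. Three narrative sections repeat the scope as a risk control: 1.3.2, 1.3.6.3 ("in this trial participants with a history of invasive cancer requiring systemic therapy will be excluded") and 2.1 ("any potential CF subjects with a history of invasive cancer requiring systemic therapy will be excluded from the study"). All five places agree with one another.

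Section 1.3.6.3 also sets out why cancer is a concern. It says: "A number of studies demonstrate homing of MSCs to primary and metastatic cancers where they may form tumor stroma". It adds that "trophic or immunosuppressive effects of MSCs could create a permissive environment for cancer development", cites work in mice on breast cancer metastasis and melanoma cell survival, and reports one randomized trial in hematologic malignancy in which leukemia relapse was 6/10 with MSCs against 3/15 without. It closes with a reassurance, "Despite these theoretical concerns, there have been no reports of *de novo* tumor formation complicating MSC infusion in humans", and two safeguards: keeping the number of passages to a minimum, and exclusion 16.

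Section 4.1 provides that anyone who meets every inclusion criterion and no exclusion criterion is entered.

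**The concern.** The safeguard is narrower than the hazard it is offered against. Homing requires a tumour to be present. Whether that tumour calls for systemic therapy, surgery or radiation plays no part in the mechanism as the protocol describes it. Yet the exclusion sorts subjects by treatment type, and the protocol gives no reason for drawing the line there.

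At stake is whether a subject with an existing invasive cancer could be infused under the written criteria without anyone having decided that this is acceptable. The study is uncontrolled, so if such a subject's cancer later progressed, the trial could not separate an effect of the cells from the course of the disease. Entry is therefore where this risk can be handled.

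**Working it through.** No design figure bears on this point. Section 15.6 justifies the 15 subjects by feasibility, not by power or precision. The check is a reading of the criteria against the hazard text, with one side calculation.

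**1. What exclusion 16 requires.** Two elements must both hold: (a) invasive cancer and (b) a requirement for systemic therapy. There is no time window and no separate clause for current or locally treated cancer.

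| Subject | (a) | (b) | Excluded by item 16? |
|---|---|---|---|
| Past invasive cancer that required systemic therapy | yes | yes | yes |
| Current invasive cancer that requires systemic therapy | yes | yes | yes, on an ordinary reading |
| Current invasive cancer needing only local treatment | yes | no | no |
| Past invasive cancer treated only by surgery or radiation | yes | no | no |

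The second row assumes that a history includes a present diagnosis. If it were read as past disease only, that row would also pass and the gap would be wider.

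**2. Whether another criterion closes the gap.** Of the 7 inclusion and 19 exclusion criteria in sections 6.2 and 6.3, only item 16 names cancer. The nearest others are:
- inclusion 3, clinical stability, which looks back 2 weeks from screening;
- exclusion 19, the investigator's judgement that the subject is unlikely to complete the study;
- the bars on immunosuppressants and on previous organ transplantation.

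The first two might lead an investigator to decline such a subject, but both involve judgement and neither is aimed at tumour risk. None of these is a categorical bar.

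**3. Whether the hazard has the same limit.** Homing and the permissive environment are stated without reference to treatment. Minimal passaging is there to limit cytogenetic abnormalities in the infused cells. It does not act on a tumour in the recipient. Of the two safeguards in section 1.3.6.3, only exclusion 16 addresses an existing tumour.

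**4. How strong the cited human signal is.** Inputs from section 1.3.6.3: 6 of 10 relapsed with MSCs and 3 of 15 without.
- Proportions: 6/10 = 60.0% and 3/15 = 20.0%, as printed.
- Odds ratio: (6 × 12)/(4 × 3) = 72/12 = 6.0.
- Fisher's exact test, with 9 relapses among 25 fixed, so C(25,9) = 2,042,975 tables:
  - Observed table: C(10,6) × C(15,3) = 210 × 455 = 95,550.
  - More relapses with MSCs (7, 8 or 9): 12,600 + 675 + 10 = 13,285.
  - Opposite tail, tables no more likely than the observed one (0 or 1): 5,005 + 64,350 = 69,355.
  - Two-sided p = (95,550 + 13,285 + 69,355)/2,042,975 = 178,190/2,042,975 = 0.087.

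The direction is as the protocol reports, but the comparison is small and falls short of the conventional 5% level. The mismatch rests on the homing statement, not on this figure.

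**The case against.** The best defence is that the limit is a reasonable proxy for risk. The only human figures cited against MSCs come from patients with hematologic malignancy undergoing stem cell transplantation, and a history of that kind meets exclusion 16. The rest of the adverse evidence in section 1.3.6.3 is largely animal or culture work, and the protocol gives no human data showing harm in locally treated cancer. It also holds contrary evidence. Section 1.3.4.3.2 reports 43 subjects with hematologic malignancies, given 1 to 5 × 10^6 MSCs/kg, without an excess of tumour progression. Sections 1.3.2 and 2.1 cite a meta-analysis that found no association with malignancy.

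Much of this stands, and it keeps the point modest. It does not close the gap. The absence of new tumours says nothing about growth of one already there. The 43 transplant subjects had received myeloablative chemo-radiation, so they do not represent untreated or locally treated cancer. A proxy may be defensible, but the protocol does not say that it is using one or why.

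Four stronger readings are tempting, and the documents do not support them.
- **Any current cancer passes.** It does not. The criterion turns on what the cancer requires, so one awaiting necessary systemic therapy is caught on an ordinary reading.
- **The subjects left in are those most exposed to the hazard.** Nothing in the protocol ranks risk by treatment type.
- **One progression among 15 subjects gives a usable rate.** Progression can occur only in someone who has or had cancer, so 15 is the wrong denominator.
- **The donor exclusions in section 9.1.10 show the same gap because they list no cancer item.** Donor cancer history is a different hazard from homing to a recipient's tumour. Donors are also screened under 21 CFR 1271 (section 4.1) and by a donor history questionnaire (section 9.4.1) whose items are not in the documents, so silence in one list does not show that the history goes unscreened.

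**Conclusion.** Exclusion 16 is narrower than the hazard in section 1.3.6.3, and no other criterion makes up the difference categorically. The gap has two parts: current invasive cancer needing only local treatment, and past invasive cancer treated only by surgery or radiation. The mismatch is clearer for the first, where a tumour is known to be present. For the second it depends on whether any tumour remains.

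This is a mismatch between a stated risk and its safeguard. It is not a contradiction between two criteria and not evidence that infusion would cause harm. The signal is unsettled (Fisher p = 0.087 in the one human comparison, no excess progression in the transplant study). The number of subjects affected cannot be calculated from the documents. It is assumed to be small, with 15 to be recruited from a centre caring for over 200 adults. The conclusion assumes a literal reading of the criterion and that a history of cancer includes a present diagnosis.

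**What to change.** Reconcile exclusion 16, in the synopsis and in section 6.3, with section 1.3.6.3. The direct way is to make the criterion turn on the presence of invasive cancer, so that at least current invasive cancer is covered regardless of treatment type. Whether past cancer treated only locally is covered, and over what period, is a clinical decision for the sponsor and no look-back is suggested here. If the sponsor prefers to keep the systemic-therapy limit, section 1.3.6.3 should say why it is adequate against the homing and permissive-environment concerns. In either case the matching sentences in sections 1.3.2, 1.3.6.3 and 2.1 should be brought into line.

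The cost is one line in two lists and up to three narrative sentences. No visit, endpoint or analysis changes. The downside is possibly losing a rare candidate.

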1.3.6.4 Rejection

MSCs are immunoevasive and non-immunogenic, which allows them to be used in allogeneic and xenogeneic transplantation. Humans have received well over 20,000 infusions of MSC, both autogeneic and allogeneic, and there have been no episodes of rejection.

1.3.6.5 Ectopic Tissue Formation

MSCs have the capability to differentiate into a number of mesodermal tissues and, possibly, tissues derived from other germ layers. Ectopic calcification and/or ossification were observed with direct injection of MSCs into infarcted mouse heart⁷⁴. Ectopic tissue formation has not been reported in any human studies. Despite being specifically sought, ectopic tissue formation was not seen in 3+ years of follow-up in 7 subjects who underwent MSC/HSC co-infusion⁶².

1.3.6.6 *Graft vs. Host Disease*

GVHD should not be an issue with removal of lymphocytes during culture expansion. In addition, allogeneic MSCs are now standard of care in pediatric patients requiring allogeneic bone marrow transplants for the prevention of GVHD.

1.3.7 Experience in Isolation and Culture Expansion of Mesenchymal Stem Cells

MSCs have been isolated and cultured in large numbers in the Cellular Therapy Laboratory of the Case Western Reserve University Center for Stem Cell and Regenerative Medicine under several INDs, including IND 11176 and IND 13917. MSCs are isolated from a BM aspirate (50-100 ml using a brisk pull) and culture-expanded according to procedures outlined in existing SOPs. Culture expanded MSCs are tested for morphology, surface antigen expression, potential microbiological contamination, and viability prior to release for infusion.

Human MSCs have been generated from approximately 3000 individual donor marrows over the past 25 years at Case Western Reserve University. Typically, $>250 \times 10^6$ MSCs can be generated from a 20-mL BM aspirate. Human MSCs propagated in culture are $\geq 95\%$ pure as judged by reactivity to MSC-specific monoclonal antibodies to CD105 and CD73⁸³. Culture conditions are specific for growth of MSCs. Adherent CD14⁺ or CD45⁺ hematopoietic cells are eliminated from the culture after the first passage. The techniques for propagating MSCs in tissue culture have been highly successful, and cultures remain free of contaminating bacteria, fungus, mycoplasma or endotoxin for at least 7 weeks (personal communication [name]).

1.3.8 Cystic Fibrosis Clinical Trial Experience at Rainbow Babies and Children's Hospital

The Cystic Fibrosis Clinical Research Center located at Rainbow Babies and Children's Hospitals/Case Western Reserve University has extensive experience in conducting clinical trials in CF. We have a long standing tradition of research since the Clinical Care Center's inception over 50 years ago. Our Research Center was one of the original 7 Centers of the Cystic Fibrosis Foundation's Therapeutics Development Network, which was established in 1998. We have participated in nearly every clinical trial in CF since that time. This Center consistently has 30 or more active CF clinical research trials approved by the Institutional Review Board (IRB). [name] is the PI on this clinical trial. [name] has been site PI on 4 clinical trials and site Co-I on several other CF clinical trials since joining the CF clinical research team over two years ago. [name] will be assisted in this study by [name] and [name], both of whom are experienced clinical investigators. [name] has published well over 100 peer reviewed manuscripts on CF clinical trials and served as site PI, site Co-I and Lead PI on dozens of multicenter clinical trials in CF. He has been instrumental in bringing several approved therapies for CF to market. In addition, [name], the previous PI on this study, will serve as a collaborator from his new institution. This Center is well-known for its excellence in clinical research.

